**Table 2 Venetoclax Dose Modifications for Non-Hematologic Toxicity**

Non-hematologic Toxicity	
Event(s)	Dose Delay or Modification
Grade 3 or 4 TLS (first episode and subsequent episodes)	

Hold all study treatments (venetoclax) until TLS resolves. The patient's next dose may be delayed for up to 28 days.

Following complete resolution of TLS, if venetoclax was held for 14 days or less, venetoclax may be restarted at the same dose or at one lower dose level as determined by the investigator based on a risk assessment (including tumor burden status) in conjunction with prophylactic hydration and uricosuric agent; hospitalization for restarting the venetoclax dose may be considered at the discretion of the investigator. Dose must be resumed at one lower dose level if interruption lasted more than 14 days.

Grade 3 or 4 non-hematologic toxicity not specifically described above	

Delay venetoclax for a maximum of 28 days.

First episode: If improvement to Grade <math>\leq</math> 1 or baseline, resume previous doses of venetoclax.

For subsequent episodes: If improvement to Grade <math>\leq</math> 1 or baseline, restart venetoclax at one dose level reduction (see Table 3).

Grade 2 non-hematologic toxicity	Delay treatment with venetoclax until resolution to Grade $\leq$ 1 (or baseline status) for a maximum of 28 days. After resolution, resume the full dose of venetoclax.
Grade 1 non-hematologic toxicity	No dose reduction or delay

TLS = tumor lysis syndrome.

**Table 3 Venetoclax Dose Reduction**

Venetoclax Current Dose Level	Venetoclax Dose Reduction
800 mg	400 mg
400 mg	200 mg
200 mg	100 mg
100 mg	Discontinue venetoclax

Gradual dose increase following resolution of toxicity leading to a dose reduction may be considered if the patient is stable for 2 weeks on the lower dose; however, if the toxicity recurs, the patient may continue treatment on the lower dose.

### 7.1.5 Infections Prophylaxis

All patients will be monitored closely for infection and treated aggressively according to institutional guidelines. If clearly indicated, anti-infective prophylaxis should be implemented at the investigator's discretion, including appropriate prophylaxis for viral, fungal, bacterial, or pneumocystis infections.

Although there is a potential for drug-drug interactions, there is likely to be limited potential clinical effects. There will be careful monitoring by the PI in such cases.

### **7.1.6                    Excluded Therapy**

- Receipt of live viral vaccines within 28 days prior to the initiation of study treatment, at any time during study treatment, or in the 30 days following last dose of study treatment
- Use of the following concomitant medications is prohibited from 7 days prior to initiation of drug treatment or during the study:
  - Strong CYP3A4 inhibitors such as fluconazole, ketoconazole, and clarithromycin
  - Strong CYP3A4 inducers such as rifampin, carbamazepine, phenytoin, and St. John's wort
  - Warfarin

As discussed in Section 8.1.2.1 detailing the use of CYP3A inhibitors and inducers with ibrutinib, for strong CYP3A inhibitors used short-term (e.g., antifungals and antibiotics for 7 days or less, e.g., ketoconazole, itraconazole, voriconazole, posaconazole, clarithromycin, telithromycin) consider interrupting venetoclax therapy during the duration of the use the inhibitor.

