#### **1.2.5.8 Drug Interactions**

##### **Concomitant Use with Other Medications**

Venetoclax should not be used with strong CYP3A inhibitors (e.g., ketoconazole, ritonavir, clarithromycin, itraconazole, voriconazole) at initiation and during ramp-up phase. Concomitant use of venetoclax with moderate CYP3A inhibitors (e.g., erythromycin, ciprofloxacin, diltiazem, fluconazole, verapamil), or strong CYP3A inducers (e.g., carbamazepine, phenytoin, rifampin, St. John's wort), or moderate CYP3A inducers (e.g., bosentan, efavirenz, etavirine) should be avoided. For patients who have completed the ramp-up phase and are on a steady daily dose of venetoclax, concomitant use of strong and moderate CYP3A inhibitors may be allowed with venetoclax dose reductions.

Venetoclax should be administered using caution with weak inhibitors or inducers of CYP3A, substrates or inhibitors of P-gp, BCRP, or OATP1B1/B3. If venetoclax is co-administered with warfarin, the international normalized ratio (INR) should be monitored closely.

Live-virus vaccines should not be given within 28 days prior to the initiation of study treatment, at any time during study treatment, or in the 30 days following last dose of study treatment.

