## 4.2 EXCLUSION CRITERIA

Patients who meet any of the following criteria will be excluded from study entry:

1. Known central nervous system lymphoma.
2. History of stroke or intracranial hemorrhage within 6 months prior to enrollment.
3. Requires anticoagulation with warfarin or equivalent vitamin K antagonists (eg, phenprocoumon).
4. Received the following agents within 7 days prior to the first dose of venetoclax or requires chronic treatment with strong CYP3A inhibitors (e.g., ketoconazole, ritonavir, clarithromycin, itraconazole, voriconazole), moderate CYP3A inhibitors (e.g., erythromycin, ciprofloxacin, diltiazem, fluconazole, verapamil), strong CYP3A inducers (e.g., carbamazepine, phenytoin, rifampin, St. John's wort) or moderate CYP3A inducers (e.g., bosentan, efavirenz, etavirine). (See Appendix 4)
5. Clinically significant cardiovascular disease such as uncontrolled or symptomatic arrhythmias, congestive heart failure, or myocardial infarction within 6 months of Screening, or any Class 3 (moderate) or Class 4 (severe) cardiac disease as defined by the New York Heart Association Functional Classification.
6. Vaccinated with live, attenuated vaccines within 4 weeks of enrollment.
7. Use of any other standard chemotherapy, radiation therapy, or experimental drug therapy for the treatment of DLBCL within 21 days of starting treatment
8. Known history of human immunodeficiency virus (HIV) or active Hepatitis C Virus or active Hepatitis B Virus infection or any uncontrolled active systemic infection or human T-cell leukemia virus 1 (HTLV-1) seropositive status or a Child – Pugh Class of B or C.
9. Any life-threatening illness, medical condition, or organ system dysfunction which, in the investigator's opinion, could compromise the subject's safety, interfere with the absorption or metabolism of ibrutinib capsules, venetoclax or rituximab or put the study outcomes at undue risk.
10. History of uncontrolled or symptomatic angina
11. Ejection fraction below the institutional normal limit
12. History of other malignancy that could affect compliance with the protocol or interpretation of results
  - Patients with a history of curatively treated basal or squamous cell carcinoma of the skin or in situ carcinoma of the cervix are generally eligible. Patients with a malignancy that has been treated, but not with curative intent, will also be excluded, unless the malignancy has been in remission without treatment for  $\geq 2$  years prior to enrollment.

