## **7.2.2 Dose and Administration of Ibrutinib**

The first dose of ibrutinib will be administered orally on Cycle 1 Day 2, of the Treatment Phase, after which ibrutinib will be self-administered daily by the subjects on an outpatient basis. Ibrutinib dosing will continue for up to a total of 24 cycles.

Ibrutinib will be dosed 0–30 minutes before the rituximab infusion and at the same time as venetoclax on days where ibrutinib, rituximab and venetoclax are administered.

Ibrutinib 560 mg (4 x 140-mg capsules) is administered orally once daily with 8 ounces (approximately 240 mL) of water at approximately the same time each day. The capsules should be swallowed intact and patients should not attempt to open, break or chew capsules or dissolve them in water. The use of strong CYP3A4/5 inhibitors/inducers, and grapefruit and Seville oranges should be avoided for the duration of the study (CYP3A4/5 list, Appendix 4). If a dose is missed, it can be taken as soon as possible on the same day with a return to the normal schedule the following day. The subject should not take extra capsules to make up the missed dose.

Ibrutinib dosing is continuous (without interruption) throughout the Treatment Phase. If Day 1 venetoclax or rituximab dosing is delayed for toxicity that does not require ibrutinib to be held for toxicity, dosing of ibrutinib should continue. If a Day 1 (of any Cycle- starting cycle 2) rituximab infusion is delayed due to scheduling delays, ibrutinib dosing should continue. Treatment will continue until disease progression or other reason for treatment discontinuation or until 24 cycles or end of study (3 years after patient enrolled).

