#### **7.2.4.2 Dose modifications for use with CYP3A inhibitors**

**Table 4: Recommended Ibrutinib Dose Modifications for use with CYP3A Inhibitors**

Patient Population	Coadministered Drug	Recommended Ibrutinib Dose
B-Cell Malignancies	
 
Moderate CYP3A inhibitor
 
	280 mg once daily Modify dose as recommended.
	
 
Voriconazole 200 mg twice daily
 
Posaconazole suspension 100 mg once daily, 100 mg twice daily, or 200 mg twice daily
 
	140 mg once daily Modify dose as recommended.

	
 
• Posaconazole suspension 200 mg three times daily or 400 mg twice daily
 
• Posaconazole IV injection 300 mg once daily
 
• Posaconazole delayed-release tablets 300 mg once daily
 
	70 mg once daily Interrupt dose as recommended.
	
 
• Other strong CYP3A inhibitors
 
	Avoid concomitant use. If these inhibitors will be used short-term (such as anti-infectives for seven days or less), interrupt ibrutinib.

Avoid co-administration with strong or moderate CYP3A inhibitors and consider alternative agents with less CYP3A inhibition.

Concomitant use of strong CYP3A inhibitors which would be taken chronically (e.g., ritonavir, indinavir, nelfinavir, saquinavir, boceprevir, telaprevir, nefazodone) is not recommended. For short-term use (treatment for 7 days or less) of strong CYP3A inhibitors (e.g., antifungals and antibiotics) consider interrupting ibrutinib therapy until the CYP3A inhibitor is no longer needed.

Reduce ibrutinib dose to 280 mg if a moderate CYP3A inhibitor must be used (e.g., fluconazole, darunavir, erythromycin, diltiazem, atazanavir, aprepitant, amprenavir, fosamprenavir, crizotinib, imatinib, verapamil, and ciprofloxacin).

Patients taking concomitant strong or moderate CYP3A inhibitors should be monitored more closely for signs of ibrutinib toxicity.

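### The CYP3A inhibitor rules conflict on classification and on what to do when an inhibitor is used anyway, and the Cycle 1 replacement rule leaves open how such patients count for DLTs

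*Combined protocol and SAP*

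**What the plan says.** The rules are spread over several sections of the protocol.

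- **Section 4.2, exclusion criterion 4** excludes patients who took strong or moderate inhibitors in the 7 days before venetoclax or who need them chronically. Fluconazole is among the "moderate CYP3A inhibitors (e.g., erythromycin, ciprofloxacin, diltiazem, fluconazole, verapamil").
- **Section 7.1.6 (venetoclax)** states: "Use of the following concomitant medications is prohibited from 7 days prior to initiation of drug treatment or during the study". The first item is "Strong CYP3A4 inhibitors such as fluconazole, ketoconazole, and clarithromycin". The same section then tells sites to consider pausing venetoclax if a strong inhibitor is used short-term (7 days or less).
- **Section 7.2.2 (ibrutinib)** says to avoid strong inhibitors for the whole study. It also says that "patients should not attempt to open, break or chew capsules". Section 7.2.1 describes one strength, 140 mg.
- **Section 7.2.4.2 (ibrutinib)** says to avoid strong and moderate inhibitors, then adds: "Reduce ibrutinib dose to 280 mg if a moderate CYP3A inhibitor must be used (e.g., fluconazole" and others). Its Table 4 gives reduced ibrutinib doses for voriconazole and posaconazole. For the higher posaconazole exposures one cell reads "70 mg once daily" and also instructs the site to interrupt the dose.
- **Section 8.1.2.1 (ibrutinib)** says to avoid both classes, and to consider pausing ibrutinib for short-term strong inhibitors. Voriconazole and posaconazole are named.
- **Appendix 4** lists fluconazole as moderate, puts voriconazole under the residual group of other inhibitors, and does not list posaconazole.
- **Section 1.2.5.8 (background)** says that after ramp-up "concomitant use of strong and moderate CYP3A inhibitors may be allowed with venetoclax dose reductions".
- **Section 12, under the DLT definitions**, replaces a subject who misses more than 4 doses of ibrutinib or venetoclax in the first cycle for reasons other than toxicity.

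**The concern.** Every patient takes both oral drugs, so rules written separately for each drug have to be workable together. Inhibitor use during treatment is also foreseeable: Section 7.1.5 leaves antifungal and antibacterial prophylaxis to the investigator.

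Two things are at stake. The first is patient safety, because a site that looks up the same anti-infective in different sections finds different instructions. The second is the primary endpoint. Each dose level is judged on DLTs in 3 to 6 patients, so whether one patient is counted or replaced can change the decision. The section a site follows can determine which of these happens.

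**Working it through.** No sample-size or power figure is involved. The check sets the passages side by side, with simple arithmetic on capsules and missed doses.

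**1. Classification of fluconazole**

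| Place | Class | Consequence |
|---|---|---|
| 7.1.6 | strong | prohibited on study |
| 4.2, criterion 4 | moderate | excluded at entry |
| 7.2.4.2 | moderate | avoid; if unavoidable, ibrutinib 280 mg |
| Appendix 4 | moderate | list only |
| 1.2.5.8 (background) | moderate | avoid; later, possible venetoclax reduction |

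That is strong once and moderate four times, three of them outside the background section. Voriconazole is strong in criterion 4 and in 7.1.6, but not in Appendix 4's strong list.

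**2. Action when an inhibitor is used**

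- *Strong inhibitor, venetoclax:* 7.1.6 gives a prohibition and then a contingency for short-term use, without saying when the contingency overrides the prohibition.
- *Short-term voriconazole or posaconazole, ibrutinib:* 8.1.2.1 says consider a pause; Table 4 gives reduced dosing. The text below Table 4 also suggests a pause for short-term strong inhibitors, so 7.2.4.2 is not consistent within itself.
- *Moderate inhibitor, venetoclax:* Section 7.1 gives no action. Only 1.2.5.8 mentions a reduction. It gives no dose and depends on a ramp-up, whereas Section 5.2 gives each cohort its assigned dose from Cycle 1 Day 2. The steps in the venetoclax reduction table (7.1.4, Table 3) are for toxicity.

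**3. Capsules** (dose divided by 140 mg)

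- 560/140 = 4, matching the stated four capsules
- 420/140 = 3
- 280/140 = 2
- 140/140 = 1
- 70/140 = 0.5, which cannot be given as an intact 140 mg capsule

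**4. DLT evaluability**

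Oral dosing runs daily from Day 2 to Day 28 of Cycle 1, or 27 doses. The replacement limit is more than 4 missed. Assume a 7-day inhibitor course in Cycle 1 for a reason other than toxicity.

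| Drug given | Section followed | Result in Cycle 1 | Missed doses | Status |
|---|---|---|---|---|
| Voriconazole | 8.1.2.1, ibrutinib paused | no ibrutinib for 7 days | 7 (> 4) | replaced |
| Voriconazole 200 mg twice daily | Table 4 | ibrutinib 140/560 = 25% of assigned dose | 0 | counted |
| Fluconazole | 7.1.6, handled as strong, venetoclax paused | no venetoclax for 7 days | 7 (> 4) | replaced |
| Fluconazole | 7.2.4.2 | ibrutinib 280/560 = 50% of assigned dose | 0 | counted |

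The two Table 4 and 7.2.4.2 rows assume that venetoclax is not also paused. A pause of 4 days or fewer leaves the patient counted in every row. The fluconazole pause row is a reading: the short-term clause in 7.1.6 does not list fluconazole among its examples, but the same section has just called it strong.

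**The case against.** The strongest reply is that the main instruction is the same throughout. Criterion 4 excludes recent or chronic users of both classes. Section 7.1.6 prohibits strong inhibitors and names fluconazole, so on that page it is barred whatever its label. Sections 7.2.2, 7.2.4.2 and 8.1.2.1 all say to avoid. This stands, and it limits the point to classification and to what happens when an inhibitor is used despite the rule.

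Three further replies stand in part.

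- Section 1.2.5.8 is background, not a treatment instruction. It is the weakest evidence and the conflict does not depend on it.
- The 70 mg row is narrow: it covers only the higher posaconazole exposures, and its cell also says to interrupt. Ibrutinib comes from commercial supply, so another strength is conceivable, but none is described.
- The replacement rule is a safeguard, since it removes patients with long non-toxicity interruptions from the DLT count. What it leaves open is shorter interruptions and interaction-driven dose reductions.

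The reply that the sections are drug-specific does not succeed, because all patients receive both drugs.

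A reader might infer that exposure at a nominal dose level is not controlled. The documents do not support that: the exclusion, the prohibition, the instructions to avoid and the replacement rule are all partial controls.

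**Conclusion.** The point holds as an internal inconsistency. The protocol gives conflicting classes and conflicting fallback actions for named anti-infectives, and one dose cell conflicts with the capsule described. As a result, patients on the same anti-infective could be handled differently and then be either counted at, or replaced from, the same dose level.

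The size of the effect on the MTD decision cannot be derived. Three figures might tempt a reader to put a number on it, and none measures this problem.

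- The 24-fold rise in ibrutinib AUC (Section 8.1.2.1) is for ketoconazole in healthy volunteers. The conflicts that change the action concern fluconazole, voriconazole and posaconazole.
- The roughly 2-fold higher venetoclax exposure (Section 7.3) comes from ibrutinib 560 mg itself and belongs to the regimen. The documents give no fold-change for venetoclax with a CYP3A inhibitor.
- At an assumed true DLT rate of 10%, a level passes with probability 0.729 + 0.243 × 0.729 = 0.906, or 0.9^5 = 0.590 if one of the first three patients is certain to have a DLT. That fall follows from any single DLT, and nothing in the documents gives the chance that an interaction causes one.

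The conclusion rests on two assumptions: that an inhibitor is sometimes used in Cycle 1 despite the rules, and that 140 mg is the only capsule strength supplied.

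**What to change.** 1. Reconcile Sections 1.2.5.8, 4.2 (criterion 4), 7.1.6, 7.2.2, 7.2.4.2 and 8.1.2.1 and Appendix 4, so that each inhibitor has one classification and compatible actions for ibrutinib and venetoclax. A single table would do this; corrected text with cross-references would also serve.
2. Make the 70 mg cell of Table 4 state one action and agree with the capsule strength supplied.
3. In Section 12, state whether a patient who receives an inhibitor in Cycle 1 and has an interruption of 4 doses or fewer, or an interaction-driven dose reduction, is evaluable for DLT or is replaced.

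Which classification, dose or action applies is a clinical decision for the sponsor. The cost is wording in one protocol amendment, with the approvals that Section 14.4 requires. The planned sample size and the escalation rules need not change.

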## **7.2                    IBRUTINIB**

All subjects in this study will receive commercial ibrutinib (Ibrutinib capsules will be from commercial supply but will be provided by Janssen Scientific Affairs, LLC) and will follow guidelines for ibrutinib dosing and toxicity management.

### **7.2.1                    Formulation, Packaging, and Storage of Ibrutinib**

Ibrutinib is an inhibitor of Bruton's tyrosine kinase (BTK). It is a white to off-white solid with the empirical formula C25H24N6O2 and a molecular weight 440.50. Ibrutinib is freely soluble in dimethyl sulfoxide, soluble in methanol and practically insoluble in water. The chemical name for ibrutinib is 1-[(3R)-3-[4-amino-3-(4-phenoxyphenyl)-1Hpyrazolo[3,4-d]pyrimidin-1-yl]-1-piperidinyl]-2-propen-1-one.

Ibrutinib capsules are provided as a hard gelatin capsule containing 140 mg of ibrutinib. Ibrutinib PO hard gelatin capsule is an oral formulation containing micronized ibrutinib and the following compendial excipients: microcrystalline cellulose (National Formulary [NF]); croscarmellose sodium (NF); sodium lauryl sulfate (NF); may contain magnesium stearate (NF).

The ibrutinib capsules will be packaged in opaque high-density polyethylene plastic bottles with labels bearing the appropriate label text as required by governing regulatory agencies. All study drug will be dispensed in child-resistant packaging. Refer to the USPI and IB for additional guidance on study drug storage, preparation and handling. Commercially available Ibrutinib will be used in this study.

## **7.2.2 Dose and Administration of Ibrutinib**

The first dose of ibrutinib will be administered orally on Cycle 1 Day 2, of the Treatment Phase, after which ibrutinib will be self-administered daily by the subjects on an outpatient basis. Ibrutinib dosing will continue for up to a total of 24 cycles.

Ibrutinib will be dosed 0–30 minutes before the rituximab infusion and at the same time as venetoclax on days where ibrutinib, rituximab and venetoclax are administered.

Ibrutinib 560 mg (4 x 140-mg capsules) is administered orally once daily with 8 ounces (approximately 240 mL) of water at approximately the same time each day. The capsules should be swallowed intact and patients should not attempt to open, break or chew capsules or dissolve them in water. The use of strong CYP3A4/5 inhibitors/inducers, and grapefruit and Seville oranges should be avoided for the duration of the study (CYP3A4/5 list, Appendix 4). If a dose is missed, it can be taken as soon as possible on the same day with a return to the normal schedule the following day. The subject should not take extra capsules to make up the missed dose.

Ibrutinib dosing is continuous (without interruption) throughout the Treatment Phase. If Day 1 venetoclax or rituximab dosing is delayed for toxicity that does not require ibrutinib to be held for toxicity, dosing of ibrutinib should continue. If a Day 1 (of any Cycle- starting cycle 2) rituximab infusion is delayed due to scheduling delays, ibrutinib dosing should continue. Treatment will continue until disease progression or other reason for treatment discontinuation or until 24 cycles or end of study (3 years after patient enrolled).

## **7.2.3 Dose Hold, Reduction or Discontinuation of Ibrutinib**

In order to continue ibrutinib at the start of a new cycle, the subject must not meet any of the criteria for ibrutinib dose modification. Treatment with ibrutinib should be withheld for any unmanageable, potentially study drug related non-hematological toxicity that is Grade 3 or higher in severity and any hematologic toxicity meeting criteria for dose hold. Subjects who require full-dose of anticoagulant treatment (eg, heparin) should have ibrutinib held until stable on anticoagulant therapy. For subjects that require an invasive procedure or surgery, PI will consider the benefit-risk of withholding ibrutinib for at least 3 to 7 days pre and post surgery depending upon the type of surgery and the risk of bleeding. Ibrutinib may be withheld for a maximum of 28 consecutive days for toxicity. Ibrutinib should be discontinued in the event of an ibrutinib toxicity lasting more than 28 days. The decision to allow patients to continue in the event of an ibrutinib toxicity lasting more than 28 days will be at PI discretion

